#### 5.3.4.3. Axitinib/Placebo Dose Reduction for Proteinuria

- If dipstick shows ≥2+ proteinuria, perform UPC. Dosing may continue while waiting for test results.
- If UPC < 2.0 is reported, continue dosing at the same dose level.

- If UPC ≥ 2.0 is reported, hold dosing and repeat UPC (interval at investigator discretion) until UPC is < 2.0. Restart axitinib/placebo at the same dose or one lower dose level at discretion of the investigator. Repeated UPC can be performed during treatment interruption at the site laboratory.
- If UPC  $\geq$  2 despite dose reduction to 1 mg BID, discontinue dosing.

Patients removed from treatment for intolerable toxicity should still be followed with regular tumor assessments until recurrence or occurrence of a secondary malignancy or start of new treatment, and for survival thereafter.

## 5.3.4.4. Axitinib/Placebo Dose Interruption for Surgery or Surgical Procedures

If a major surgery or an invasive intervention (eg, endoscopy) is required, treatment with axitinib/placebo must be interrupted at least 24 hours before the procedure and the patient BP should be monitored closely for hypotension. Depending on the investigators assessment patients may resume axitinib/placebo 7 days after surgery/invasive intervention, assuming wound has completely healed and no wound healing complications (eg, delayed healing, wound infection or fistula).

## **5.3.5.** Compliance

Patients will maintain diaries to include missed or changed doses. Pill counts on returned study drug bottles should be performed.

## 5.4. Drug Storage and Drug Accountability

Axitinib/placebo will be supplied for the study. Study drug will be shipped to the study sites.

The investigator, or an approved representative (eg, pharmacist), will ensure that all axitinib/placebo is stored in a secured area, under recommended storage conditions and in accordance with applicable regulatory requirements. Drug should be stored at controlled room temperature (ie, 15-30°C) and protected from light and moisture.

To ensure adequate records, all axitinib/placebo will be accounted for in the CRFs and drug accountability inventory forms as instructed by sponsor. Unless otherwise authorized by sponsor, at the end of the clinical trial all drug supplies unallocated or unused by the patients must be returned to sponsor or its appointed agent (eg, a contract research organization).

Axitinib is considered a hazardous drug (due to possible reproductive toxicity), and should be handled according to the recommended procedures described in the current edition of the ASHP, Technical Assistance Bulletin on Handling Cytotoxic and Hazardous Drugs, AHFS Drug Information (1999) and its references. Procedures described in each institution's pharmacy or hospital standard operating procedure manual should be followed when handling hazardous drugs.

## 5.5. Prior/Concomitant Therapy

## 5.5.1. Prior/Concomitant Medication

No other chemotherapy or experimental anticancer medications will be permitted while the patient is on study. Any disease requiring other forms of systemic anticancer therapy will be cause for discontinuation from study treatment.

Patients may receive loperamide or other medications for treatment or prophylaxis of potential diarrhea. Anti-inflammatory or narcotic analgesics may be offered as needed. Patients with fever or infection may undergo diagnostic tests and treated with antibiotics as appropriate and may receive therapeutic colony-stimulating factors as appropriate. Erythropoietic agents such as epoetin or darbepoetin may be used at the discretion of the treating investigator. Packed red blood cell and platelet transfusions should be administered as clinically indicated. Low-dose oral steroids (defined as ≤5 mg per day prednisone or equivalent), short course of oral steroids (defined as < 5 consecutive days or topical or inhaled steroids at any dose) may be taken during the study.

Patients who need to be on anticoagulant therapy before or during study treatment should be treated with low molecular weight heparin. If low dose heparin cannot be administered, the administration of coumadin or other coumarin derivatives or other anti-coagulants may be allowed; however, appropriate monitoring for bleeding risk including prothrombin time/international normalized ratio (PT/INR) should be performed.

In vitro studies with human liver microenzymes and recombinant CYP enzymes indicated that axitinib metabolism was primarily mediated by the drug-metabolizing enzyme CYP3A4/5, and to a lesser extent by CYP1A2. Additionally, the drug also undergoes N-glucuronidation in liver microsomes of some species. Clinically, there is likelihood that axitinib plasma concentrations may be increased in the presence of co-administered potent inhibitors of the CYP3A4/5 and glucuronosyltransferase enzymes. In a healthy volunteer study, ketoconazole, a potent CYP3A4/5 inhibitor, produced a 2-fold increase in plasma exposure and a 1.5-fold increase in peak plasma concentration of axitinib. Therefore a potential exists for drug-drug interactions with CYP3A4/5 inhibitors such as grapefruit juice, ketoconazole, itraconazole, clarithromycin, atazanavir, indinavir, nefazodone, nelfinavir, ritonavir, saquinavir, and telithromycin. Caution should be exercised in patients receiving axitinib in combination with these and other potent CYP3A4/5 inhibitors until appropriate clinical drug interaction studies are performed. If a strong CYP3A4/5 inhibitor must be co-administered, based on investigator judgment, the dose of study drug (axitinib/placebo) should be decreased by one or more dose levels.

Axitinib metabolism may be induced in patients taking CYP3A4/5 or CYP1A2 inducers (rifampin, dexamethasone, phenytoin, carbamazepine, rifabutin, rifapentin, phenobarbital, and St. John's wort) and this may reduce axitinib plasma concentrations. Patients who require concomitant treatment with potent CYP3A4/5 or CYP1A2 inducers are not eligible for the study. Since CYP1A2 is also known to be induced in chronic smokers, there is likelihood that axitinib plasma concentrations may be reduced in these individuals. (Note: these patients are not excluded from enrolment, however.)

The ability of axitinib to increase concentrations of coadministered drugs was also investigated in studies with human liver microsomes. At expected therapeutic plasma concentrations (0.01 to 1.0  $\mu g/mL$ ), axitinib appears most likely to inhibit the drug metabolizing enzymes CYP1A2 and CYP2C8, 2 enzymes not frequently observed as predominant drug metabolizing enzymes. Theophylline, and tacrine are among the few drugs whose plasma concentrations are likely to be increased by axitinib.

Axitinib is highly bound to proteins in human plasma (99.5% bound at concentrations between 0.2 to 20  $\mu$ g/mL). Therefore, drug interactions with other agents that are also highly bound to plasma proteins are a possibility.

Axitinib is not likely to have drug-drug interactions with commonly used antihypertensive agents belonging to the class of ACE inhibitors including angiotensin II receptor antagonists (enalapril, captopril, losartan, valsartan), beta-blockers (atenolol, metoprolol, labetalol), or diuretics (hydrochlorothiazide, furosemide). Within the class of calcium channel blockers, verapamil, and to a lesser extent nifedipine, nicardipine, and diltiazem have a potential for increasing axitinib plasma concentrations, due to CYP3A4/5 inhibition and should not be used as first choice in antihypertensive treatment. Other calcium channel blockers (amlodipine, bepridil, felodipine) are less likely to raise axitinib plasma levels.

The above information is based on preclinical data from studies using human and animal metabolizing enzyme systems.

All prior/concomitant medications and blood products, as well as interventions (eg, analgesic use or paracentesis) received by patients from the time the patient has signed informed consent until 28 days after last treatment will be recorded on the CRF. Anti-tumor therapy should be recorded even after 28 days after last treatment.

[figure not shown]
## 5.5.2. Concomitant Radiotherapy

Investigators are encouraged to await the result of the IRC assessment before making treatment decisions for patients who require palliative radiotherapy because of suspected recurrence or occurrence of a secondary malignancy unless clinical considerations require immediate intervention eg, in the case of brain metastases. In the event that an investigator determines recurrence or occurrence of a secondary malignancy based on local imaging and/or local histo-/cytopathology reports, the patient must continue to receive tumor assessments until the IRC determines recurrence or occurrence of a secondary malignancy.

#### 6. TRIAL PROCEDURES

#### 6.1. Screening

Figure 3 Screening Procedures

\*: IRC review of imaging to be returned within 2 weeks post submission of images.

## 6.1.1. Screening Procedures between Nephrectomy and Starting Treatment

One rescreening is acceptable. Patient with screening values/findings outside ranges described in the protocol may, at the discretion of the investigator, have one repeat determination performed and if the repeat value satisfies the criterion they may continue in the screening process. Only the specific out of range value/finding should be repeated (not the entire panel).

- a. Medical history including oncologic history, history of other disease processes (active or resolved), signs and symptoms, concomitant medications and treatments, illnesses and demographics.
- b. Local histopathology confirmation of eligibility is required.
- c. Pre-surgery images are requested, if available or whenever possible should be submitted for IRC review.
- d. ECOG PS ascertained at the time of nephrectomy (just prior to nephrectomy) is desired.
- e. Local and IRC review of tumor imaging including CT or MRI of the brain, chest, abdomen and pelvis and other applicable sites of disease. CT scans are expected to be with intravenous and/or oral contrast. CT or MRI of the chest, abdomen and pelvis must be performed at least 3 weeks after nephrectomy. Results of the IRC assessment must be awaited before randomizing patients. Thus, images should be submitted for IRC review before Week 8 post-nephrectomy to allow for return of the results before Week 12 and in the event a repeat scan is needed. Brain CT or MRI within 12 weeks prior to randomization is acceptable regardless of whether it is before or after nephrectomy. Bone scan (either Tc-99 or positron emission tomography (FDG-PET)) can be performed if clinically indicated.

## 6.1.2. Screening Procedures Within 2 Weeks Prior to Randomization

a. Physical examination of major body systems.

\*\*: Randomization will occur no sooner than 4 weeks post-nephrectomy and no later than 12 weeks post-nephrectomy. This figure shows the latest case after nephrectomy. Study treatment should be started within 7 days after randomization.

- b. Body weight, height and vital signs (temperature, 2 BP readings separated by at least 1 hour, pulse rate).
- c. Laboratory tests.
  - Hematology: Hgb, white blood cell count (WBC), ANC, lymphocyte count and platelet count.
  - Chemistry: Total bilirubin, AST, ALT, alkaline phosphatase, albumin, total protein, LDH, sodium, potassium, chloride, calcium, phosphate, BUN/Urea, creatinine, glucose.
  - Urine dipstick for protein (patients with  $\geq 2+$  protein will have UPC).
  - Pregnancy test, if applicable. Urine pregnancy test will be conducted at sites for females of childbearing potential only. If positive, then serum test should be conducted at central laboratories.
- d. Triplicate 12 lead ECGs to be performed two weeks prior to randomization. Three consecutive 12 lead ECGs (with a 10 second rhythm strip) will be collected at screening to determine the mean QTc interval. If the QTc interval is prolonged (>500msec), the ECG should be re-read by a cardiologist at the site for confirmation.
- e. Assessment of concomitant medications and treatments.
- f. Study Registration/Randomization.

#### 6.2. Trial Period

For the purposes of this study, unscheduled assessments may occur coincident with safety events, early discontinuation of study treatment, early study termination, suspected recurrence, or suspected occurrence of the secondary malignancy between protocol-specified study visits.

## 6.2.1. Treatment Procedures First Cycle

#### 6.2.1.1. Day 1

The following procedures must be performed pre-dose. It is not necessary to repeat the Day 1 procedures if treatment is not started on the same day as randomization:

- a. Physical Examination of major body systems.
- b. Body weight and vital signs (temperature, BP, pulse rate). Patients who have 2 sBP readings, separated by at least 5 minutes, greater than 140 mm Hg, or 2 dBP readings, separated by at least 5 minutes, greater than 90 mm Hg, will not start treatment.
- c. ECOG PS.

- d. Thyroid function tests: TSH, free T3, free T4.
- e. Assessment of adverse events.
- f. Assessment of concomitant medications and treatments.

## 6.2.1.2. Day 15

Assessments should be performed via telephone contact or visit. In case of telephone contact, only adverse events assessment should be performed.

- a. Physical Examination of major body systems.
- b. Body weight and vital signs (temperature, 2 BP readings separated by at least 5 minutes, pulse rate).
- c. Thyroid function tests: TSH (Free T3 and free T4 should be performed for any patient who has an elevated TSH at Day1 or the previous visit.) Hypothyroidism should be treated per standard medical practice to maintain euthyroid state with a normal TSH.
- d. Assessment of adverse events.
- e. Assessment of concomitant medications and treatments.

## **6.2.2.** Treatment Procedures Subsequent Cycles

Assessments other than tumor imaging should be done at Day 1 of every cycle (4 weeks) until Cycle 5 Day 1, then every 8 weeks thereafter starting from Cycle 7 Day 1.

- a. Physical examination of major body systems.
- b. Body weight and vital signs (temperature, 2 BP readings separated by at least 5 minutes, pulse rate).
- c. ECOG PS.
- d. Laboratory tests.
  - Hematology: Hgb, WBC, ANC, lymphocyte count and platelet count.
  - Chemistry: Total bilirubin, AST, ALT, alkaline phosphatase, albumin, total protein, LDH, sodium, potassium, chloride, calcium, phosphate, BUN/Urea, creatinine, glucose.
  - Urine Dipstick for protein (patients with  $\geq 2+$  protein will have UPC).
  - Thyroid function tests: TSH. Hypothyroidism should be treated per standard medical practice to maintain euthyroid state with a normal TSH (TSH, Free T3

and free T4 should be performed on the next visit for any patient who has an elevated TSH.).

- e. Tumor imaging including CT or MRI of the chest, abdomen, and pelvis should be performed every 16 weeks for the first 3 years from the initiation of study treatment. Additional imaging and/or local histo-/cytopathology confirmation, if clinically indicated, of potential disease sites should be performed whenever recurrence or occurrence of a secondary malignancy is suspected. Brain CT or MRI with contrast or bone scan (confirmatory imaging in addition to bone scan may be required), if clinically indicated.
- f. Assessment of concomitant medications and treatments.
- g. Assessment of study drug compliance/accountability.
- h. Assessment of adverse events and tumor-related signs and symptoms.

## 6.2.3. End of Study Treatment/Withdrawal from treatment Procedures

At the end of the study or at withdrawal from treatment, the following procedures should be performed if they were not performed within 7 days of the end of the study or at withdrawal:

- a. Physical examination of major body systems.
- b. Body weight and vital signs (temperature, 2 BP readings separated by at least 5 minutes, pulse rate).
- c. ECOG PS.
- d. Laboratory tests.
  - Hematology: Hgb, WBC, ANC, lymphocyte count and platelet count.
  - Chemistry: Total bilirubin, AST, ALT, alkaline phosphatase, albumin, total protein, LDH, sodium, potassium, chloride, calcium, phosphate, BUN/Urea, creatinine, glucose.
  - Urine Dipstick for protein (patients with  $\geq 2+$  protein will have UPC).
  - Thyroid function tests: TSH (Free T3 and free T4 should be performed for any patient who has an elevated TSH in the previous visit.)
- e. Tumor imaging including CT or MRI of the chest, abdomen, and pelvis and other applicable sites of disease. Local histo-/cytopathology confirmation, if clinically indicated, of potential disease sites should be performed whenever recurrence or occurrence of a secondary malignancy is suspected. Brain CT or MRI with contrast or bone scan if clinically indicated. At the end of the study or at withdrawal, the tumor imaging should be performed if they were not performed within 8 weeks of the

end of the study or at withdrawal for patients who discontinue treatment for reasons other than disease progression.

- f. Assessment of concomitant medications and treatments.
- g. Assessment of study drug compliance/accountability. Patients must return all used and unused study drug bottles to the clinical site.
- h. Assessment of adverse events and tumor-related signs and symptoms.

## 6.3. 28 Days Post Treatment Follow-Up Visit

Patients should continue to be evaluated up to 28 days after the last dose of study drug. At the post-treatment follow-up visit, the following procedures should be performed:

- Assessment of adverse events and tumor-related signs and symptoms.
- Assessment of concomitant medications and treatments.

During this period, the outcome of adverse events with a date of onset during the study period should be reevaluated, and any new adverse events should be recorded. All serious adverse events, and those non-serious adverse events assessed by the investigator as possibly related to study drug, should continue to be followed even after patient withdrawal from study. These adverse events should be followed until they resolve, or until the investigator assesses them to be "chronic" or "stable".

## 6.4. Recurrence or occurrence of secondary malignancy and Survival Follow-Up

Follow-up for recurrence or occurrence of a secondary malignancy must be collected at each clinic visit as per protocol. All patients will be followed up (regardless of the duration of treatment) until the time for final analysis, every 16 weeks for the first 3 years from initiation of study treatment (also, at the end of treatment) and every 6 months thereafter for the remainder of follow-up period\*. If new anti tumor therapy is initiated for either recurrence or occurrence of a secondary malignancy at any time during this period, this and all other pertinent data obtained should be recorded on the appropriate CRFs. The final analysis of primary endpoint (DFS) will be performed when approximately 245 DFS events have been reached.

\* Patients who complete 3-year treatment will be followed up for DFS every 6 months from the date of CT or MRI at the end of study treatment.

Patients who withdraw from treatment before DFS events will be followed up for DFS every 16 weeks from the date of CT or MRI at the withdrawal. After 3 years from initiation of study treatment, CT or MRI for DFS will be performed every 6 months from the first scan date that is performed after more than 3 years from initiation of study treatment.

All patients will be followed up for OS status (regardless of the duration of treatment) approximately every 16 weeks from DFS events until the time for final DFS analysis. Survival status can be ascertained by telephone contact.

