- 21. **Follow-up Survival Status**: Survival status information should be collected, approximately every 16 weeks (+/- 2 weeks) from DFS events, until the time for final DFS analysis. Survival information can be done via telephone contact.

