#### 3. TRIAL DESIGN

This is a prospective, randomized, double-blind placebo controlled Phase 3 trial of oral axitinib starting at 5 mg twice daily vs. placebo given for up to 3 years, with a minimum of 1 year. The dose may be increased or decreased depending on individual patient tolerance of axitinib.

A total of approximately 700 patients will be randomized in a 1:1 ratio between axitinib vs placebo. Patients should begin study treatment within 7 days after randomization. Randomization will occur no sooner than 4 weeks post-nephrectomy and no later than 12 weeks post-nephrectomy.

Follow-up for recurrence (distant or local recurrence of RCC) or occurrence of a secondary malignancy (occurrence of a second primary cancer other than RCC) must be collected at each clinic visit as per protocol. All patients will be followed up (regardless of the duration of treatment) until the time for the final analysis, every 16 weeks for the first 3 years from initiation of study treatment (also, at the end of treatment) and every 6 months thereafter for the remainder of the follow-up period, by clinic visit (See Section 6.4 for further details).

All patients will be followed up for OS status (regardless of the duration of treatment) every 16 weeks until the time for final DFS analysis. Survival status can be ascertained by telephone contact. At the time of final DFS analysis, OS results will be analyzed and summarized.

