## 9.1. Sample Size Determination

The patient population in this study can be classified into 4 risk groups:

- a. pT2, pN0 or pNx, M0 and ECOG 0-1
- b. pT3, pN0 or pNx, M0 and ECOG 0-1
- c. pT4, pN0 or pNx, M0 and ECOG 0-1
- d. Any pT, pN1, M0 and ECOG 0-1

Sample size was determined based on the analysis on the primary endpoint, DFS.

The sample size for this study was calculated based on the following assumptions:

- Time to DFS event follows an exponential distribution.
- The percentage of patients randomized from the 4 risk groups, 2-year DFS rates for placebo arm and axitinib arm are assumed below

Categories	Risk groups	Percentage of patients	2-year DFS rate for placebo arm	2-year DFS rate for axitinib arm
1	a. pT2/pN0 or pNX/M0 b. pT3/pN0 or pNX/M0	90%	70%	79%
2	c. pT4/pN0 or pNX/M0	1%	35%	61%
3	d. Any pT/pN1/M0	9%	33%	51%

The assumptions of 2-year DFS rates for the placebo arm and axitinib arm are equivalent to the assumptions of hazard ratios to be 0.66, 0.47, and 0.61 for the 3 categories 1, 2 and 3 respectively. Given the assumed distribution of patients randomized (1:1) into each of these categories, the overall hazard ratio is estimated to be 0.654.

Based on the above assumptions, a minimal number of 245 DFS events will be required to provide 90% power to detect the statistical difference in DFS with HR  $\leq$  0.654 between the two treatment groups with 2-sided significance level of 0.05.

Applying a 1:1 randomization and a planned accrual period of 24 months, a maximum follow-up period of 60 months (5 years), and an assumed 23% drop-out rate by 18 months, it was estimated that approximately 700 patients will be enrolled.

The final analysis will take place when approximately 245 DFS events are observed.

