**Statistical Analysis Plan**

---

thereafter for the remainder of the follow-up period. The total duration of the study from first subject in to final analysis is estimated to be 5 years.

All subjects will be followed for OS status (regardless of the duration of treatment) every 16 weeks until the time of final DFS analysis. Survival status can be ascertained by telephone contact. At the time of final DFS analysis, OS results will be analyzed and summarized.

A single interim analysis (IA) of efficacy and safety will be performed after approximately 184 DFS events (approximately 75% of the total number of required events as assessed by the independent review committee [IRC]) have occurred. If the event occurrence pace is much slower than anticipated, the IA could be performed when less than 184 events are observed (<75% of the total required) at the sponsor’s discretion with the Data Monitoring Committee’s (DMC) consensus. To protect the integrity of the study and to preserve the Type 1 error, a fraction of alpha will be spent at the interim analysis of DFS based on an O’Brien-Fleming spending function. The stopping boundaries will be calculated based on the actual number of events at the time of the interim analysis.

The objectives of the interim analysis will be:

- To assess the safety, including any unexpected toxicity.
- To allow for early stopping of the trial due to futility.
- To assess the efficacy of the study drug to allow stopping of trial for success of efficacy.

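### Protocol 6.4 and footnote 21 time the survival contacts from the DFS event, so contactable patients who stop DFS visits event-free have no scheduled contact, contrary to Section 3 and SAP 3.1

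*Protocol*

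**What the plan says.** The documents contain two survival-contact rules.

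**Every patient, with no starting event.** Protocol Section 3: "All patients will be followed up for OS status (regardless of the duration of treatment) every 16 weeks until the time for final DFS analysis". The Trial Design part of the Protocol Summary says the same. SAP 3.1: "All subjects will be followed for OS status (regardless of the duration of treatment) every 16 weeks until the time of final DFS analysis".

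**Starting from the DFS event.** Protocol 6.4 opens with all patients but then sets the timing as "approximately every 16 weeks from DFS events until the time for final DFS analysis". Footnote 21 of the Schedule of Assessments: "Survival status information should be collected, approximately every 16 weeks (+/- 2 weeks) from DFS events". The Schedule grid marks survival status only in the Survival Follow-Up column, not in the DFS Follow-up column.

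Other relevant text:

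- Protocol 6.4 keeps event-free patients on DFS visits every 16 weeks to year 3 and every 6 months after that, whether or not they are still on treatment.
- Protocol 6.5 asks sites to make every effort to contact a patient who misses a scheduled visit, and to document outcome in any circumstance if possible.
- Protocol 5.3.4.2 and 5.3.4.3 follow patients removed for intolerable toxicity with tumor assessments until recurrence, secondary malignancy or new treatment, and for survival after that.
- Protocol 6.5.1 foresees patients who stop treatment but permit follow-up. Protocol 6.5.2 ends all data collection when consent for future information is withdrawn.
- SAP 6.2 continues DFS and OS follow-up after treatment stops.
- Protocol 7.1.2 and SAP 5.2 censor OS at the last date known alive. SAP 7.2.1 tests OS at two-sided 0.0499 if DFS is significant.

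**The concern.** Sites schedule contacts from Section 6.4 and the Schedule of Assessments, not from the design overview. Under those passages, vital status before a DFS event is a by-product of the DFS visits, and the separate survival contacts take over after the event. That works while the patient keeps attending. A patient who declines further scans and visits, has no DFS event and is still willing to be telephoned falls between the two: the visits have stopped and the contacts have no date to start from.

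OS for that patient is then censored at the last time the site happened to know the patient was alive. Patients with a DFS event are traced on a schedule, while patients who left without one are traced only by best effort. If leaving is related to toxicity or declining health, which is plausible but not quantified in the documents, the censoring is informative. OS is the only secondary efficacy endpoint and carries a formal test, so its completeness matters.

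**Working it through.** **1. Which rule covers which patient.**

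| Patient | Section 3 / SAP 3.1 | 6.4 / footnote 21 |
|---|---|---|
| Event-free, attending, years 0–3 | every 16 weeks | every 16 weeks, through DFS visits |
| Event-free, attending, after year 3 | every 16 weeks | every 6 months, through DFS visits |
| After a DFS event | every 16 weeks | every 16 weeks |
| Event-free, stopped DFS visits, contactable | every 16 weeks | no scheduled recurring contact |
| Consent for further information withdrawn | none possible | none possible |

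The fourth row is the gap. The second is a smaller mismatch that needs no drop-out.

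**2. Planning basis.** The concern disputes no planning number. As a check on the inputs, the Freedman formula at HR 0.654, 90% power and two-sided 0.05 gives 241 events against the stated 245. With the planned looks (0.0194 and 0.0442 at 75% and 100%), 245 events give 90.1% power using the Freedman drift.

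**3. Ceiling on the exposed group.** Inputs from Protocol 9.1: 700 patients 1:1, 24-month accrual (taken as uniform), exponential DFS, the 2-year DFS rates by category, and "an assumed 23% drop-out rate by 18 months".

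- By 18 months: 0.23 × 700 = 161 patients.
- Drop-out hazard: δ = −ln(0.77)/18 = 0.01452 per month, assumed constant and equal in both arms.
- DFS hazards: λ = −ln(2-year rate)/24. Placebo: 0.01486, 0.04374, 0.04619. Axitinib: 0.00982, 0.02060, 0.02806. Category weights w: 0.90, 0.01, 0.09.
- Expected drop-outs without an event by month T, per arm: the sum over categories of 350·w·[δ/(λ+δ)]·{1 − [e^(−(λ+δ)(T−24)) − e^(−(λ+δ)T)] / [24(λ+δ)]}.
- Largest term at T = 57 (placebo, category 1): λ+δ = 0.02938, δ/(λ+δ) = 0.494, bracket = 0.728, so 350 × 0.90 × 0.494 × 0.728 ≈ 113.

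| Month | Drop-outs without event | DFS events |
|---|---|---|
| 48 | 226 | 217 |
| 54 | 246 | 236 |
| 57 | about 255 (121 placebo, 134 axitinib) | 244 |
| 60 | 264 | 251 |

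Month 57 is about when the 245 events are projected. 255/700 = 36%. The difference between arms comes only from the lower DFS hazard assumed for axitinib, since δ is the same in both.

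**4. Illustration of deaths outside scheduled contact.** The documents give neither the contactable share nor mortality after drop-out, so both are assumptions here. The model leaves about 653 person-years between drop-out and month 60. With 25% to 100% contactable and 2% to 10% mortality a year:

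- low end: 653 × 0.25 × 0.02 ≈ 3 deaths;
- high end: 653 × 1.00 × 0.10 ≈ 65 deaths.

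Best-effort tracing would recover some of these. The width of the range shows that the documents cannot fix the effect on OS.

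**The case against.** The two rules can be read together. Clinic visits establish vital status before the event and telephone contacts do so afterwards, which fits the separate columns in the Schedule. For attending patients this delivers the promised 16-week interval for three years. The sentence in 6.4 also opens with all patients, and no passage says that contacts start only at a DFS event.

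Three stronger readings are tempting, and the documents do not support them.

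- *Event-free drop-outs get no survival calls at all.* Section 6.5 asks for every effort to contact a patient who misses a scheduled visit. Sections 5.3.4.2 and 5.3.4.3 start survival follow-up at new treatment for toxicity withdrawals, and SAP 6.2 continues OS follow-up. What is missing is a recurring schedule. The toxicity clause gives no interval and does not reach a patient who refuses scans and starts no new treatment. Section 6.5 is qualified by feasibility, and the SAP statement gives sites no timetable.
- *OS will be biased by arm because toxicity drop-out is heavier on axitinib.* No passage gives drop-out by arm, and the calculation assumes equal hazards. The split of 121 and 134 is not evidence for this.
- *About 255 patients will lack OS data because of this wording.* That number counts every modelled drop-out, including patients nobody may call and patients nobody can find. It also carries an 18-month allowance forward to month 57.

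The post-year-3 mismatch also deserves little weight. A death learned of at a 6-monthly contact still carries its true date, so the longer interval mainly shortens last-known-alive times.

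What stands is the textual conflict, and the lack of any scheduled contact for event-free patients who stop visits but remain reachable.

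**Conclusion.** The passages conflict and must be reconciled. Followed literally, 6.4 and footnote 21 leave one identifiable group, contactable patients who stop DFS visits without an event, outside the 16-weekly survival contacts that Section 3, the Summary and SAP 3.1 promise. The consequence is a risk, not a certainty, of early and possibly informative censoring of an endpoint that is tested if DFS succeeds. A difference between arms is not shown.

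The exposed group is at most about 255 of 700 (36%) by month 57. This rests on a constant drop-out hazard beyond 18 months, equal hazards in both arms, uniform accrual and the planned DFS rates. The number who could actually have been called is smaller by an amount the documents do not give. This is more than a missing detail, because a stated operational rule contradicts the design section and can lose survival data that a telephone call would recover.

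**What to change.** 1. In Protocol 6.4 and footnote 21, replace the DFS-event starting point with: *from the DFS event, or from the last DFS visit if the patient stops DFS visits without an event (unless consent for further information is withdrawn)*. This brings both passages into line with the Summary, Section 3 and SAP 3.1 for the patients now left out.
2. At the DFS data cut-off, check vital status once for all patients who are not known to be dead and have not withdrawn consent.
3. For event-free patients after year 3, either state that the 6-monthly visit serves as the survival contact or add calls between visits. This is for consistency and has little analytic effect.

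Cost: amended wording and some additional telephone contacts, a method the protocol already allows. No scans or clinic visits are added. The cut-off check is new work that Section 3 does not already promise, and it should be budgeted as such.
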